3.4 Visit 3 - Study Pump Training and Run-In Period

Visit 3 may occur concurrently with Visit 1 and 2.

Subjects will have supervised training on the study pump as described below.

Study staff will review subject's pump parameters by manual review and/or download of personal insulin pump.

All subjects will have a run-in period on the study pump of up to two weeks duration. Subjects who have had prior experience with the study pump may skip or require a shorter run-in period. The pump run-in period may overlap with any required CGM run-in period. Pump training will include:

 The subject will be fully instructed on the study insulin pump. A qualified staff member or pump trainer will conduct the training and in particular discuss differences from their home pump in important aspects such as calculation of insulin on board and correction boluses. Additional topics not be limited to but may include: infusion site initiation, cartridge/priming procedures, setting up the pump, changing batteries, navigation through menus, bolus procedures including stopping a bolus, etc.

- The study team will assist the subject in study pump infusion site initiation and will start the subject on the study pump. The study pump will be programmed with the subject's usual basal rates and pump parameters. The subject's personal pump will be removed.
- The subject will be supervised with the study pump during at least one meal or snack bolus to ensure subject understanding of the pump features.
- The subject will be encouraged to review the literature provided with the pump, infusion sets, and other pump related supplies after the training is completed.

3.5 Visit 4 – Closed Loop Training Visit

Visit 4 will occur just prior to starting the first session of Closed-Loop Control to ensure that the training is in close proximity to the initiation of the system in closed loop control (for Group B this will occur earlier than Group A).

Visit 3 and 4 may occur concurrently for inControl users. For subjects starting on the Tandem-G6 system, Visit 3 and 4 will be concurrent.

Visit 4 will consist of a ~5-10 hour training session in a transitional setting at a research house, hotel or clinic during which the subject will be trained to use the system to control the study pump, including meal announcement, meal bolusing, exercise, and switching back and forth between Pump (open-loop) mode and Stopped mode. Subjects may be asked to view study materials at home (e.g. User Guides and/or study videos on the Use of the AP System) prior to coming to Visit 4. This visit may shorter than 5-10 hours depending on the subject's proficiency with the system as well as prior experience.

A serum or urine pregnancy test will be collected for all premenopausal women who are not surgically sterile.

Prior to initial use, the system will be initialized with each subject's individual parameters, including carbohydrate ratio, correction factor, and basal rate pattern.

Study team members will train the subject in performing specific tasks including the following:

- The study team will confirm the pump parameters entered in the system with the subject.
- How to switch the system between Pump mode (open-loop, preprogrammed basal insulin delivery) and Stopped mode depending on circumstances. For the Tandem-G6 system, this will consist of turning Control-IQ off.
- How to calibrate the CGM unit during the study.
- How to access the CGM trace on the user interface.
- How to activate the meal screen of the system any time insulin will be given with a meal or any time additional correction insulin is desired.
- How to inform the system of hypoglycemia treatment on the user interface.
- What to do in when engaging in strenuous exertion
- How to perform blood ketone testing and perform rescue therapy actions with the glucagon kit

- The subject will be assessed for understanding of the system interface and how to react to safety/alert messages.
- The subject will be given a AP system User Guide relevant to their system (Appendix A-10) as a reference.

The subject must be able to complete system-related tasks independently to be eligible to continue in the study.

3.6 Visit 5 - AP System Run-In phase: Home Use in Pump Only (Open Loop) Configuration

Eligible subjects who have not had recent use of the system (more than ~2 weeks of use in the past 6 months or more than ~2 months of use in the past year) will complete up to 2-week home use period with the full system in pump only (open loop) configuration where no closed loop algorithms are activated. Subject will be instructed not to start closed loop during this run-in phase. Subjects who have had prior experience with the AP system as defined above will not be required to do Visit 5. Subjects who are demonstrating proficiency, as determined by the study physician, may have a shorter open loop run-in phase with a minimum of 5 days duration Criteria for proficiency is listed in section 3.11.

For the inControl system, remote monitoring will be available during this period for the purposes of data collection and ad hoc assessment of system performance by study team. The study team will be available for the subject to contact during this phase. Study staff will contact the subject and review data on the Remote Monitoring once daily. The subject may contact the study staff at any time.

For the Tandem-G6 system, remote monitoring will not be available. Study staff will contact the subject daily to assess difficulties with the use of the system. The subject may contact the study staff at any time. If the study team requires additional information, the subject may be asked to upload the pump at home so that the study can review data on the t:connect website.

3.7 Visit 6 + Visit 7 + Visit 8 Washout Following Completion of the Each Study Phase

At the completion of the each phase of the study, subjects will have up to a two week washout prior to proceeding to the next phase.

First Phase: Group A 8 weeks of SAP; Group B 8 weeks of USS +SAP(d) Second Phase: Group A 8 weeks of USS +SAP(d); Group B 8 weeks of USS + CLC(d) Third Phase: Group A 8 weeks of USS + CLC(d); Group B 8 weeks of USS +SAP (d) Fourth Phase: Group A 8 weeks of USS + SAP(d); Group B 8 weeks of SAP

Visit 6 may occur concurrently with Visits 3, 4 and 5. During this time, subjects may continue on the study pump if Visit 4 has been completed or switch to their own personal pump. Subjects will either come to the study site or complete the following locally: HgbA1c, and psychometric questionnaires (Appendix A-11)

Individual Structured Interviews [Optional]: Subjects will be asked to participate in an individual structured interview after using the AP system (Group A= after visit 7, 8, 9; Group B=after visit 6, 7, 8).

These structured interviews will be audiotaped to assist staff in recording subjects' responses. These interviews may be conducted in person or over the phone. The audio recordings will be labeled with the study subject ID number and will be stored with other study documentation.

Data will be downloaded from study devices, glucometer and personal pump (during SAP) by one of several methods: locally by the subject and sent to study staff, by study staff at time of a visit or devices not in use being mailed to the study staff for downloading.

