We plan to randomize up to 110 patients with type 1 diabetes into two different treatment sequences:

Group A following the sequence $SAP \rightarrow USS+SAP(d) \rightarrow USS+CLC(d) \rightarrow USS+SAP(d)$, and **Group B** following the sequence $USS+SAP(d) \rightarrow USS+CLC(d) \rightarrow USS+SAP(d) \rightarrow SAP$.

These treatment modality sequences are presented in the figure below, and are color coded to match the color-coding of active control modules relevant to each treatment modality presented in Figure 1:

Figure 1: Design of One 11-month Study Session

Each treatment modality will continue for 8 weeks – sufficient time to address the following specific aims:

SA1: Dinner/Night CLC achieved by USS+SAP(d) will be superior to SAP alone in terms of: (1) Improved HbA1c without increasing the risk for hypoglycemia; (2) Reduced incidence and risk for hypoglycemia overnight, and (3) Reduced fear of hypoglycemia and improved diabetes quality of life scores.

SA2: CLC during the day achieved by USS+CLC(d) will preserve the benefits of USS+SAP(d) and will be superior to USS+SAP(d) in terms of: (1) Increased time within target range of 70-180mg/dl during the day; (2) Reduced risk for hypoglycemia, particularly during and after exercise, and (3) Reduced postprandial glucose variability.

SA3: CLC system acceptance evaluated by individual structured interviews and technology acceptance scores will be: (1) Superior, for USS+SAP(d) compared to SAP alone, i.e. adding USS in the evening and overnight will increase patients' acceptance of CLC, and (2) Marginally inferior, for USS+CLC(d) compared to USS+SAP(d); i.e. some patients would prefer SAP alone during the day due to perceived increased system complexity.

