6.1 Analysis Plan

Statistical Analysis: The overall analysis will follow Intention-to-treat approach and will use Generalized Linear Mixed Models (e.g. those available in IBM SPSS) including fixed factors following the factorial designs presented in study figure for the specific aims listed below, and random effects reflecting patients' attrition rate.

Metrics:

- (i) Five HbA1c determinations approximately 10 weeks apart;
- (ii) Eight-week sequences of CGM data accompanied by BG self-monitoring readings and recording of the timing of events such as meals and exercise through the GUI
- (iii) Psychometric questionnaires administered concurrently with HbA1c, and
- (iv) Individual structured interview and qualitative/quantitative technology acceptance assessments. CGM data will be used to compute established metrics of risk for hypoglycemia, e.g. the Low BG Index (LBGI), glucose variability, and BG dynamics, as presented in our review of statistical tools for CGM data analysis.

Primary Hypothesis by Specific Aims of the Study

Specific Aim 1: Overnight CLC achieved by USS+SAP(d) will be superior to SAP alone in terms of: (1) Improved HbA1c without increasing the risk for hypoglycemia; (2) Reduced incidence and risk for hypoglycemia overnight, and (3) Reduced fear of hypoglycemia and improved diabetes quality of life scores.

Specific Aim 2: CLC during the day achieved by USS+CLC(d) will preserve the benefits of USS+SAP(d) and will be superior to USS+SAP(d) in terms of: (1) Increased time within target range of 70-180mg/dl during the day; (2) Reduced risk for hypoglycemia during and after exercise, and (3) Reduced postprandial glucose variability.

Specific Aim 3: CLC system acceptance evaluated by an individual structured and technology acceptance scores will be: (1) Superior, for USS+SAP(d) compared to SAP alone, i.e. adding USS overnight will increase patients' acceptance of CLC, and (2) Marginally inferior, for USS+CLC(d) compared to USS+SAP(d); i.e. some patients would prefer SAP alone during the day due to perceived increased system complexity.

Primary Outcomes

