Specific Aim 1: The **primary outcome** is improvement in diabetes control on USS+SAP(d) vs. SAP alone as defined by reduced risk for hypoglycemia (Time <70 mg/dL by CGM) without increase in HbA1c. Repeated Measures ANOVA with covariate will assess this effect. Inversely, comparing HbA1c with covariate overnight Time <70 mg/dL by CGM will address SA1-2, while comparing the psychometric questionnaire scores pre-post treatment will address SA1-3.

Specific Aim 2: The **primary outcome** is improved time within the target range of 70-180mg/dl during the day on USS+ CLC(d) vs. USS+SAP(d). Repeated Measures ANOVA following the study design outlined will assess this effect. SA2-2 will be addressed

comparing frequency of hypoglycemia within the post-exercise periods recorded by the system; SA2-3 will be addressed using Variability-Grid Analysis, and SA-4 will be addressed by a sub-analysis limited to those who did not achieve HBA1c≤7.5% during the first 3 months of the study.

Specific Aim 3: will be addressed by comparing structured interviews and technology acceptance scores along the two sequences of treatment modalities specified in the study design: treatment escalation for Group A and de-escalation for Group B. Analyzing the random effect of patient attrition will shed additional light on system acceptance.

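### Eight-week phases leave earlier glycemia in each phase-end HbA1c, so the no-increase HbA1c condition of Specific Aim 1 is easier to pass than intended

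*Combined protocol and SAP*

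**What the plan says.** Section 1.1: "Each treatment modality will continue for 8 weeks – sufficient time to address the following specific aims". No reason is given for HbA1c in particular.

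Section 3.7 gives the order of phases. Group A has SAP, USS+SAP(d), USS+CLC(d), USS+SAP(d). Group B has USS+SAP(d), USS+CLC(d), USS+SAP(d), SAP. Between phases, "subjects will have up to a two week washout prior to proceeding to the next phase", which sets a maximum and no minimum. During washout, "subjects may continue on the study pump if Visit 4 has been completed or switch to their own personal pump"; whether closed loop is then off is not stated. HbA1c belongs to these visits ("Subjects will either come to the study site or complete the following locally: HgbA1c, and psychometric questionnaires"), with no day fixed within the washout.

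Section 6.1 lists "Five HbA1c determinations approximately 10 weeks apart". It defines the SA1 primary outcome as less CGM time below 70 mg/dL "without increase in HbA1c", and it also lists better HbA1c as the first item of SA1. The analysis is a repeated-measures ANOVA with a covariate. The written text names no carry-over term and does not say which of the two USS+SAP(d) phases enters the SA1 contrast.

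**The concern.** HbA1c averages glycemia over a period that may be longer than 8 weeks. A value taken at the end of a phase then mixes that phase with what came before, and the order of phases makes this matter in two ways:

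- In both groups one USS+SAP(d) phase comes straight after USS+CLC(d) (Group A phase 4, Group B phase 3), so its HbA1c holds some of the 24-hour closed-loop effect.
- Group B's SAP phase follows USS+SAP(d), so its HbA1c holds some of the treatment it is compared with. Group A's SAP phase follows usual care.

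The no-increase condition guards against buying less hypoglycemia with higher average glucose. A contrast pulled toward zero weakens that guard. For the superiority item on HbA1c, the same mixing can hide part of a benefit, or credit evening and overnight control with something that 24-hour control achieved.

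**Working it through.** **The plan's own timing.** Eight weeks of phase plus two of washout gives the stated 10-week HbA1c spacing. Four phases and three washouts take 4×8 + 3×2 = 38 weeks. Three run-ins of up to two weeks each (section 1.5.2) bring this to 44, the lower end of the 44–50 weeks in section 3.12. So about two weeks of washout is the usual plan, although zero days is allowed. There is no planned HbA1c difference to reproduce: section 6.2 does not name the endpoint behind its effect size.

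**Assumptions.** Let w be the weight of the 8-week phase in an HbA1c drawn on its last day. The documents give no kinetics, so I use a range. The weight on time before the phase, 1−w, is:

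- exponential memory with half-life h weeks, 0.5^(8/h): 0.157 at h = 3 and 0.397 at h = 6;
- linearly declining weights over T days, ((T−56)/T)²: (34/90)² = 0.143 and (64/120)² = 0.284.

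This is about 14–40%, so I take w = 0.60–0.85. Set SAP, usual care and washout to 0, USS+SAP(d) to d, and USS+CLC(d) to d+g. Only the preceding phase is remembered.

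**No washout, both USS+SAP(d) phases pooled.**

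- Group A: USS+SAP(d) gives wd and d+(1−w)g, and SAP gives 0. Contrast: [(1+w)d+(1−w)g]/2.
- Group B: the same two USS+SAP(d) values, but SAP gives (1−w)d. Contrast: Group A's minus (1−w)d.
- Average: **wd + (1−w)g/2**.

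| w | pooled contrast | first USS+SAP(d) phase only |
|---|---|---|
| 0.60 | 0.60d + 0.20g | 0.40d |
| 0.73 | 0.73d + 0.135g | 0.595d |
| 0.85 | 0.85d + 0.075g | 0.775d |

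Setting wd + (1−w)g/2 equal to d gives g = 2d. Below that, the pooled contrast is shrunk.

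**First USS+SAP(d) phase only (last column).** Group A gives wd and Group B gives wd − (1−w)d, so the average is (3w−1)d/2. The credit from USS+CLC(d) goes, but the shrinkage is greater.

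**With a washout.** Let v be the weight left on the phase before the washout. Group A's contrast is wd + v(d+g)/2 and Group B's is that minus vd, so the average is **wd + vg/2**. The d term is still w. With the 120-day linear weights and 14 days, v = (50/120)² = 0.174:

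- zero days: 0.716d + 0.142g on average; d terms 0.858 (Group A) and 0.574 (Group B);
- 14 days: 0.716d + 0.087g on average; d terms 0.803 and 0.629.

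Washout reduces the credit and the gap between groups, and leaves the average shrinkage where it was. The g needed to offset the shrinkage becomes 2(1−w)d/v = 2×0.284d/0.174, about 3.3d.

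**Check with the whole past weighted, not one phase only** (half-lives of 3–6 weeks; linear weights over 90 or 120 days). The pooled contrast as a fraction of d is:

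- g = 0: 0.58–0.86 with 0 days of washout, 0.59–0.86 with 14, 0.60–0.86 with 28;
- g = d: 0.66–0.93 with 0 days, 0.66–0.88 with 14.

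**Opposite signs.** Suppose USS+SAP(d) raises HbA1c by d = 0.2 and USS+CLC(d) adds g = −0.3, with w = 0.73 and no washout (illustrative values). The pooled contrast is 0.73×0.2 − 0.135×0.3 = 0.146 − 0.0405 = 0.1055. About 47% of the rise is hidden.

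**The case against.** A reader might infer that the missing minimum washout is the fault and that a full two weeks would cure it. The documents do not support that. The 10-week spacing points to about two weeks as usual, and the shrinkage of d is essentially the same at 0 and 14 days. Phase length is the cause.

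A reader might also infer that the contrast is always too small by 15–40%, or that USS+SAP(d) is certain to be credited with part of USS+CLC(d). Neither follows. The 15–40% applies to the pooled contrast at g = 0. When d and g have the same sign the two distortions oppose each other, and without washout they cancel at g = 2d. The credit arises only if the return USS+SAP(d) phases are pooled, which section 6.1 leaves open.

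The strongest defence is that the main efficacy measures do not have this problem. CGM time below 70 mg/dL and daytime time in range are recorded within each phase and carry no HbA1c memory, so the documents do not support saying that the primary hypoglycemia result is biased in this way. In addition, the model's fixed factors follow a study figure that is not shown, so period or sequence factors cannot be ruled out. Both points stand. They do not rescue the HbA1c condition: it is half of the SA1 primary outcome, and no written analysis of it is free of carry-over.

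Replacing HbA1c with CGM glucose outright would be a trade-off. Section 3.9 names the Dexcom G4 for SAP, while section 1.4 pairs the Tandem system with the G6, so the sensor may change between phases. HbA1c does not depend on the sensor.

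**Conclusion.** The concern holds for HbA1c, with 8-week phases as the cause. On an assumed w of 0.60–0.85, the USS+SAP(d) against SAP contrast recovers about 60–85% of d, plus a USS+CLC(d) credit if the return phases are pooled: (1−w)g/2 without washout, vg/2 with one. Using only the first USS+SAP(d) phase removes the credit but leaves 40–78% of d without washout. The no-increase condition is therefore easier to pass than intended, most of all when d raises and g lowers HbA1c.

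The size rests on kinetics that the documents do not give, on sampling at phase end, and on glycemia during washout returning to its SAP level. This is a worthwhile, inexpensive improvement to the analysis plan and does not invalidate the trial.

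**What to change.** In section 6.1:

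1. Keep HbA1c, but before concluding that there was no increase, also require no increase in mean CGM glucose over the later weeks of each phase (for example weeks 2–8). Record the sensor model per phase, and repeat the analysis in subjects who used the same sensor throughout.
2. State which USS+SAP(d) phases enter the SA1 contrast.
3. Add the randomized first-phase HbA1c comparison (Group A on SAP against Group B on USS+SAP(d), adjusted for baseline HbA1c) as a sensitivity analysis. It is free of carry-over from study treatment. It still estimates only about w·d, because pre-study care remains in the value, so it complements the CGM check and cannot replace it.
4. Record the length of each washout and the system mode used in it.

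The cost is SAP wording, two further analyses of data already collected, and a little extra recording. The downsides are a second condition to meet, possible sensor differences between phases, and lower precision in the first-phase analysis, which is a between-group test with about half the subjects in each arm.

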3.8 Visit 9 - End of Study Visit

At the completion of the final phase of the study, subjects will complete their final visit. Subjects will resume their personal pump. Subjects will either come to the study site or complete the following locally: HgbA1c, questionnaires, and may participate in an individual structured interview.

Data will be downloaded from study equipment, glucometer and personal pump (during SAP) by one of several methods: locally by the subject and sent to study staff, by study staff at time of a visit or equipment mailed to the study staff for downloading.

3.9 Study Procedures during SAP

- Study subjects will be using the study CGM (Dexcom G4) and either their home pump or study pump for 8 weeks. Subjects using the Tandem-G6 system during AP phases will use their home pump during SAP.
- Subjects will be following their usual home insulin parameters. There are no predictive algorithms running for insulin administration.
- Subjects will be requested to use their personal glucometer or study glucometer for all fingersticks including CGM calibrations.
- Subjects will perform their usual activities and manage their diabetic regimen per their usual routine.
- Study staff will be available at any time for the study subject to contact.
- Staff will contact the subject once a month after the first month.

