1.4 Closed-Loop Control System

A general description of the Artificial Pancreas Platform devices identified below will be used in the Closed-Loop Control System. New generations of CGMs and insulin pumps with embedded inControl-AP could become available for inclusion in this trial and could be used providing these new developments do not change the core functionality of the system.

For the inControl Platform, (see Figure 4-Panel A):

- inControl Diabetes Management Platform a smart-phone Artificial Pancreas medical platform;
- CGM study CGM connected to the AP using low power Bluetooth communication protocols;
- Insulin Pump insulin pump connected to AP system via wireless Bluetooth.
- Remote Monitoring Server connected to inControl Cloud via 3G or local Wi-Fi network, and
- Modular Closed-Loop Control Algorithm Running on the AP system, which is of Controlto-Range (CTR) class

We have successfully completed a pilot study of the Tandem t:slim X2 with Control-IQ Technology. This pilot study included 5 adults (mean HbA1c 6.5%) using the system between 36-48 hours, and was successfully completed with 86% mean time in target range of 70-180 mg/dL and 2.8% median time below 70 mg/dL. The system maintained connectivity 98% of the intended

time in closed-loop. Given the positive results from this pilot study, we now plan to incorporate t:slim X2 with Control-IQ Technology in this protocol as well.

For the Tandem-G6 configuration, (see Figure 4-Panel B):

The Closed-Loop Control System contained in t-slim X2 with Control-IQ Technology is described in Master File MAF-2032/A003 and has been approved in G170255 and G170267. Control-IQ Technology is derived from inControl previously described in IDE# G160097, G160181, G150240 and G140169/S010. The CLC is an "artificial pancreas" (AP) application that uses advanced closed loop control algorithms to automatically manage blood glucose levels for people with Type 1 Diabetes. The system modulates insulin to keep blood glucose in a targeted range. The system components include the t:slim X2 with Control-IQ Technology and the Dexcom CGM G6 (Fig. 4-B).

Figure 4. AP System Components: Panel A – G4+Roche pump configuration; Panel B – G6+Tandem Control IQ

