1.5.2 Protocol Summary

For the proposed studies, the AP system will be deployed with different functionalities at different stages of the trial, resulting in variation in what the subject will be responsible for and what the system will drive. A trial outline is contained in Figure 1 and visits detailed in Figure 5. **Study Phases without the AP system**

CGM Run-in Phase: Study participants will begin with a maximum 2 week run-in period during which they will have a CGM (i.e. sensor-augmented pump therapy or CGM+CSII) but otherwise be on their usual diabetes management with respect to BG monitoring, pump basal rates, insulin-to-carbohydrate ratios and correction factors. This is necessary because some of the study participants will not have had experience with CGMs in the past.

Study Pump Run-in Phase: All subjects will have a run-in period on the study pump of up to two week duration. Subjects who have had prior experience with the study pump may either skip this run-in phase or may require a shorter run-in period depending on their proficiency with the study pump.

Sensor-Augmented Pump (SAP) Therapy: During this phase, the subject is on the study CGM and their personal insulin pump. There are no predictive or control algorithms. The subjects will administer basal and bolus insulin using their usual home insulin parameters.

Study Phases with the AP System

AP system Run-In Phase: Subjects who have not had recent use of the system (more than approximately 2 weeks of use in the past 6 months or more than 2 months of use in the past year) will complete an up to 2-week home use period with the full system in pump only (open loop) configuration where no closed loop algorithms are activated. Subjects who have had prior experience with the system as defined above will not be required to do Visit 5.

USS+SAP (d): USS Virginia plus SAP during the day (d). Subjects will be using the study pump and CGM with the AP system in Pump mode (open loop only, no closed loop algorithms running). The subject will activate the USS Virginia Closed-Loop Control as early as pre-dinner but is expected to activate CLC by bedtime. The subject will continue in Closed-Loop Control until the time of awakening in the morning. The USS will monitor CGM and insulin-on-board data and predicts the patient's risk of hypoglycemia and adjust insulin delivery accordingly.

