3.10 Study Procedures during USS + SAP(d) and USS + CLC(d)

The subject will be wearing the study CGM, the study pump and utilizing the AP system for 8 weeks. Subject will be doing fingerstick testing using their personal glucometer or study provided glucometer.

For USS + SAP(d): The subject will be instructed to activate closed-loop operation each evening any time between just before eating dinner and prior to bedtime. The subject will be instructed to switch back to open-loop mode upon waking up in the morning.

For USS +CLC(d): The subject will be instructed to remain in closed-loop operation for 24 hours.

While using the closed loop system, the subject will be instructed to avoid deviating from his/her regular daily routine in regards to diet and exercise and to maintain his or her usual sleep schedule during the course of the study. The subject will specifically be asked to avoid consuming more than 3

alcoholic drinks in any one day. The subject will also be instructed to avoid use of closed-loop mode during periods of illness with an elevated temperature >101.5 degrees Fahrenheit, periods of significant illness, or during periods of use of medications such as epinephrine for the emergency treatment of a severe allergic reactions or asthma attack in addition to use of oral or injectable glucocorticoids. The subject will be asked to put the system in exercise mode when engaging in strenuous exertion.

The total duration during each of these phases will be 8 weeks of AP system use regardless of whether CLC was activated or not. If a subject was off the system entirely and unable to use the system (e.g. in Stopped Mode) on one or more days due to illness or other factors such as extended travel, the use period may be extended at investigator discretion to obtain 8 weeks of use.

3.11 Monitoring when the AP system is in Use during Visit 5, USS + SAP(d) and USS + CLC(d)

Throughout the study, the study subject will be given contact information for study team members and can contact the study team at any time.

During the first use of the system at visit 5 and following completion of Visit 5 (second phase for Group A and first phase for Group B), the following procedures will be in place:

- The study team will contact the subject daily for the first week.
- The study team will review the Remote Monitoring System once daily for the first week (if using inControl).

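### Section 3.9 names the Dexcom G4 for SAP with no sensor exception for Tandem-G6 subjects, whose AP phases use the G6; nothing requires the same sensor across the SA1 comparison

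*Combined protocol and SAP*

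**What the plan says.** Section 3.9 sets the equipment for the SAP phase: "Study subjects will be using the study CGM (Dexcom G4) and either their home pump or study pump for 8 weeks". Its next sentence turns to the Tandem configuration, but only for the pump: "Subjects using the Tandem-G6 system during AP phases will use their home pump during SAP". Section 1.4 describes that configuration: "The system components include the t:slim X2 with Control-IQ Technology and the Dexcom CGM G6". The Figure 4 caption there pairs sensors and pumps as "Panel A – G4+Roche pump configuration; Panel B – G6+Tandem Control IQ".

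For both AP conditions, Section 3.10 says: "The subject will be wearing the study CGM, the study pump and utilizing the AP system for 8 weeks". Section 1.5.2 describes SAP in equally general terms: "During this phase, the subject is on the study CGM and their personal insulin pump".

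Three other places bear on the sensor. Section 1.4 allows newer CGMs into the trial if the system's core functionality is unchanged. Section 4.4.3 attaches a Dexcom G4 label to the calibration rule. Section 3.11 mentions a Dexcom G5 once, for some inControl subjects.

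Section 3.7 places SAP first for Group A and last for Group B: "Fourth Phase: Group A 8 weeks of USS + SAP(d); Group B 8 weeks of SAP". In Section 6.1 the SA1 primary outcome compares USS+SAP(d) with SAP on CGM time <70 mg/dL, without an increase in HbA1c. That section lists no sensor or platform term and no analysis by sensor.

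**The concern.** For the hypoglycemia part of the SA1 primary, the CGM is the measuring instrument. A crossover protects the comparison when each subject is measured in the same way under each condition. If Section 3.9 is followed to the letter, a Tandem-G6 subject's SAP data come from one sensor generation and all AP data from another. A difference between the two in how much time they record below 70 mg/dL would then be read as an effect of closed-loop control. It could exaggerate the benefit or hide it.

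**Working it through.** **1. Sensor by phase for a Tandem-G6 subject, as written** (Sections 1.4, 3.7, 3.9, 3.10)

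| Sequence | Phase 1 | Phase 2 | Phase 3 | Phase 4 |
|---|---|---|---|---|
| Group A | SAP, G4 | USS+SAP(d), G6 | USS+CLC(d), G6 | USS+SAP(d), G6 |
| Group B | USS+SAP(d), G6 | USS+CLC(d), G6 | USS+SAP(d), G6 | SAP, G4 |

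Sensor follows condition in both rows. Putting SAP first in one group and last in the other balances period, not sensor.

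**2. Effect on the SA1 contrast.** Take complete data and a linear model with subject, period and condition effects. The least-squares estimate of USS+SAP(d) minus SAP is then

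½ × [(A, phase 4 − phase 1) − (B, phase 4 − phase 1)].

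Let d be the G6-minus-G4 difference in measured time <70 mg/dL. In affected subjects the sensor adds +d to the Group A change and −d to the Group B change. Period effects cancel, but the sensor part is ½ × [d − (−d)] = d. The USS+CLC(d) versus USS+SAP(d) contrast comes from phases 2 and 3, all on the G6, so its shift is 0.

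**3. Can a model separate it?** This was checked by the rank of the design matrix with 10 subjects per sequence (20 subject + 3 period + 2 condition = 25 columns).
- All subjects on Tandem-G6: adding a sensor column gives 26 columns with rank still 25. Sensor is fully aliased.
- Half on each platform: 26 columns, rank 26. A sensor term can be estimated, but only because the model assumes the same treatment effect on both platforms.
- Half on each platform with platform-by-condition terms (27 columns, rank 27): adding sensor gives 28 columns, rank 27. It is aliased again.

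**4. Pooled size.** Sections 1.5.1 and 6.2 give 76 completers of 110 randomized at up to 31% attrition (110 × 0.69 = 75.9, which agrees). Section 2.1 gives 64, but only the affected share matters. With equal sequences the pooled shift is share × d. The number of Tandem-G6 subjects is not stated, so the counts below are assumptions.
- 8 of 76: 8/76 = 0.11, shift 0.11 × d
- 19 of 76: 19/76 = 0.25, shift 0.25 × d
- 38 of 76: 38/76 = 0.50, shift 0.50 × d

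**5. For scale only.** The overnight pilot in Section 1.2 (10 subjects) had 1.56% versus 0.55% of time below 70 mg/dL, a difference of 1.01 points (p=0.06). A pooled shift of one tenth of that, 0.101 points, would need d of 0.101/0.105 = 0.96, 0.101/0.25 = 0.40 or 0.101/0.50 = 0.20 points. The one-tenth mark is arbitrary, and the documents do not say whether any such d is realistic.

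**The case against.** The strongest reply is that the G4 label in Section 3.9 is left over from before the Tandem system was added, so no Tandem-G6 subject would wear a G4. Several places fit this:
- Sections 1.5.2 and 3.10 speak only of the study CGM.
- Section 3.3 provides one round of study CGM training, and no later visit adds training on a second generation.
- Section 1.4 admits newer CGMs.
- Section 4.4.3 carries the same G4 label under a rule meant for the whole study, although Tandem AP phases use a G6. The label is therefore not a reliable statement of what everyone wears.

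It can also be said that Section 1.4 describes the closed-loop system and does not set the SAP sensor, so the two sections are not strictly contradictory.

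This makes leftover text plausible but does not settle it. Section 3.9 names Tandem-G6 subjects in its very next sentence and excepts only their pump. The new-device clause permits another sensor without withdrawing the G4 instruction. Nowhere is the same sensor required in SAP and AP phases.

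A reader might go further and infer that no analysis could ever separate sensor from treatment. That holds within Tandem-G6 subjects. In the pooled sample a sensor term can be estimated if the treatment effect is assumed common to both platforms. A reader might also extend the point to inControl subjects on a G5. The single mention in Section 3.11 does not show that any of them would wear a different sensor in SAP, so it is only another item to reconcile.

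**Conclusion.** The concern holds conditionally. If Section 3.9 is followed as written, sensor generation and condition coincide in Tandem-G6 subjects. A between-sensor difference d then shifts the time <70 mg/dL part of the SA1 primary by d in those subjects and by their share times d overall. If the G4 label is un-updated and these subjects wear a G6 in SAP, there is no shift, but the plan still lacks a rule that ensures this.

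The documents do not support a claim that the SA1 result is biased by a known amount or in a known direction: d, its sign and the number of Tandem-G6 subjects are all absent. The multipliers assume complete data, equal sequences, common period effects and no carryover. HbA1c does not come from the CGM and is not affected. The SA2 primary compares two AP phases and is not affected if a subject's system and sensor stay constant.

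The plan should be changed because prevention is cheap, and later separation depends on an assumption that the data cannot check.

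**What to change.** - Reconcile Sections 1.4, 3.9, 3.11 and 4.4.3 on which CGM is worn in each phase.
- Replace the named model in Section 3.9 with a rule that each subject wears the same CGM generation in SAP as in the AP phases, whichever it is. Apply the same rule to the new-device clause in Section 1.4.
- Record the sensor model for each subject and phase.
- If any subject's phases have already used different sensors, keep the intention-to-treat analysis as primary. As a supportive analysis, report the SA1 time <70 mg/dL contrast separately for same-sensor and mixed-sensor subjects, and state that the split also reflects pump and AP platform.

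If the G4 label is simply leftover text, correcting it and stating the rule is enough.

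The cost is a wording amendment and one data field per phase. SAP will need supplies of the matching sensor generation, there is less freedom to change sensor mid-participation, and SAP phases already completed cannot be matched. The supportive split is imprecise. With 8, 19 or 38 of 76 completers mixed (assumed) and equal variances, the standard error relative to the full sample is √(76/68) = 1.06, √(76/57) = 1.15 or √(76/38) = 1.41 times in same-sensor subjects. In mixed-sensor subjects it is √(76/8) = 3.08, √(76/19) = 2.00 or √(76/38) = 1.41 times.
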